2.3 Sample Size and Study Population

Participants will be a convenience sample of approximately three hundred sixty (360) opioid dependent patients leaving detoxification or short-term residential units at sites participating in CTN-0051. Approximately 60 participants will be recruited at each of approximately six sites.

Since this study utilizes a convenience sample and the objectives are to simply describe opioid use post-discharge, only detectable effect sizes were calculated (i.e., no sample size calculations performed). These effect sizes considered the evaluation of the association between post-baseline opioid use and a binary covariate such as gender, and use of medication-assisted treatment. Results of the effect size calculations are shown in Section 13.2.

[figure not shown]

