##### 3.2.4 Detectable Effect Sizes

Table 1 summarizes detectable effect sizes for the two outcomes: (a) time to first opioid use, and (b) time to first regular opioid use. The detectable hazard ratios (HRs) are calculated for various values of the standard deviation of the outcome measure and the overall percent of participants who had (a) used opioids or (b) regularly used opioids during the eight week follow-up period. Total sample sizes of 280, 320 and 360 were considered. If the target sample size of 360 is reached, and 60-70% of participants use or regularly use opioids by the week 8 follow-up visit, then there will be at least 80% power to detect a HR of approximately 1.46 with a type I error rate of 5%. On the other hand if only 320 participants are enrolled, then the detectable HR is around 1.50 and for 280 participants, then the detectable HR is around 1.40-1.75.

**Table 1.** Detectable hazard ratios for the outcomes measures time to (a) first opioid use, and (b) first regular opioid use

Total Sample Size	Detectable Hazard Ratio	Power (%)	Proportion of Participants who Used Opioids/ Regularly Used (%)	Standard Deviation of the Number of Days to First Opioid Use/Regular Use
280	1.75	83%	60%	0.4
	1.40	82%	70%	0.5
320	1.50	81%	60%	0.5
	1.47	83%	70%	0.5
360	1.47	82%	60%	0.5
	1.45	84%	70%	0.5

Table 2 summarizes detectable effect sizes for the outcomes based on the number of days of opioid use during the eight weeks post-discharge to the community of the study. The detectable mean differences for the two-sample *t*-test are calculated for various values of the group-specific mean and standard deviations of the outcome measure. Total sample sizes of 280, 320 and 360 were considered. If participants in one group use opioids on average two weeks out of the month, then we can detect a difference of 1.5 use days with at least 80% power (assuming a type I error rate of 5%) if the target sample size of 360 is achieved. Similarly, if participants in one group use approximately three weeks out of a month, then we can detect a difference of 1.5 days. With 320 participants enrolled, a mean difference of 1.5 days can still be detected with at least 80% power, but the detectable difference increases to 2.8 days with a total sample size of 280.

Table 2. Detectable differences in means for the number of days of opioid use during the eight weeks of follow-up				

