### 3.3 Software

All analyses will be performed utilizing SAS® version 9.3 or higher. All statistical tests will be conducted at the 5% Type I error rate (two-sided). When multiple tests are conducted, the chance of finding a significant difference in one of the tests, when in fact no difference exists, is greater than the stated Type I error rate. The investigators are aware of the multiple testing issues and will interpret results with caution and use confidence intervals where possible.

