#### **5.5.1 Statistical Significance**

There are no hypotheses being evaluated in this observational study with solely descriptive primary objectives, thus no formal statistical testing will be conducted. Exploratory comparisons will be made via modeling as described in Section 5.5.

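### Table 1 overstates power for 280 participants: a hazard ratio of 1.40 with 70% events has about 65% power, not 82%; the standard deviation column also looks mislabelled

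*SAP*

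**What the plan says.** SAP 3.2.4 and Protocol 13.2.3 carry the same Table 1 of detectable hazard ratios for time to first use and time to regular use. At 70% events and a standard deviation of 0.5 it prints:

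- 280 participants: hazard ratio 1.40, power 82%
- 320 participants: hazard ratio 1.47, power 83%
- 360 participants: hazard ratio 1.45, power 84%

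The text summarises the table by sample size. It gives about 1.46 for 360, then says "if only 320 participants are enrolled, then the detectable HR is around 1.50", and then "for 280 participants, then the detectable HR is around 1.40-1.75".

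On the last column, the text says "The detectable hazard ratios (HRs) are calculated for various values of the standard deviation of the outcome measure", and the column heading reads "Standard Deviation of the Number of Days to First Opioid Use/Regular Use". Its entries are 0.4 in one row and 0.5 in the other five. Protocol 2.3 describes the same calculations differently: "These effect sizes considered the evaluation of the association between post-baseline opioid use and a binary covariate such as gender".

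On sites, SAP 1.2 and 3.2.2 say five. SAP 3.2.3 says about six with about 60 participants each, and SAP 1.6 and 3.2.1 keep a total of about 360.

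**The concern.** The smallest sample is credited with the smallest detectable effect. From 320 to 280 participants, at the same event proportion and standard deviation, both the number of events and the hazard ratio fall, yet the printed power falls by only one point. A reader would conclude that 280 participants can detect 1.40 with over 80% power, a smaller effect than the plan offers for 320 or 360.

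The column label matters because the table cannot be checked or reused without knowing what 0.4 and 0.5 measure. Half a day is not a credible standard deviation for time to use over eight weeks of follow-up.

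**Working it through.** **Inputs.** Sample size N, event proportion P, standard deviation, hazard ratio (HR) and printed power are from Table 1. The two-sided 5% level is from SAP 3.3, and the Cox model from SAP 5.5. The binary covariate is from Protocol 2.3.

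**Formula (assumed, since none is stated).** Power = Φ(√(N × P) × SD × ln HR − 1.96), with SD read as that of the covariate. For a binary covariate, 0.5 = √(0.5 × 0.5) is a 50:50 split and 0.4 = √(0.2 × 0.8) is a 20:80 split.

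**Reproducing the table.** The range allows for rounding of the HR by ±0.005.

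| N | P | SD | HR | Events | √events × SD × ln HR | Computed power (range) | Printed |
|---|---|---|---|---|---|---|---|
| 280 | 60% | 0.4 | 1.75 | 168 | 2.901 | 82.7% (82.3-83.1) | 83% |
| **280** | **70%** | **0.5** | **1.40** | **196** | **2.355** | **65.4% (64.4-66.3)** | **82%** |
| 320 | 60% | 0.5 | 1.50 | 192 | 2.809 | 80.2% (79.6-80.9) | 81% |
| 320 | 70% | 0.5 | 1.47 | 224 | 2.883 | 82.2% (81.5-82.9) | 83% |
| 360 | 60% | 0.5 | 1.47 | 216 | 2.831 | 80.8% (80.1-81.5) | 82% |
| 360 | 70% | 0.5 | 1.45 | 252 | 2.949 | 83.9% (83.2-84.5) | 84% |

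For the disputed row: √196 = 14; 14 × 0.5 × ln 1.40 = 7 × 0.3365 = 2.355; 2.355 − 1.96 = 0.395; Φ(0.395) = 65.4%. A log-rank simulation of 20,000 runs gave 65.0%.

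**Check that does not depend on the meaning of the SD column.** If power depends on √events × ln HR, the disputed row can be scaled from its neighbours at the same 70% and 0.5.

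- From N = 320 (83%, so 1.960 + 0.954 = 2.914): the factor is √(196/224) × (0.3365/0.3853) = 0.935 × 0.873 = 0.817. Then 2.914 × 0.817 = 2.381, and Φ(2.381 − 1.960) = 66.3%.
- From N = 360 (84%, so 1.960 + 0.994 = 2.954): the factor is √(196/252) × (0.3365/0.3716) = 0.882 × 0.906 = 0.799. Then 2.954 × 0.799 = 2.359, and Φ(2.359 − 1.960) = 65.5%.

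**Other readings of the disputed row.**

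- One-sided 5%: 76.1%.
- Freedman's formula: 64.6% two-sided, 75.4% one-sided.
- SD 0.4: 47.0%.
- All 280 counted as events: 80.4%, still not 82%, and against the row's own 70%.
- SD needed for 82%: 2.875 / (14 × 0.3365) = 0.61, above the maximum of 0.5 for a binary covariate.

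**What the row can support.** With 196 events and SD 0.5, HR 1.49 gives 79.7%, 1.50 gives 81.0% and 1.51 gives 82.2%. Detectable HR = exp(2.802/7) = 1.49 at 80% power and exp(2.875/7) = 1.51 at 82%. HR 1.40 at 82% power needs 2.875² / (0.25 × 0.3365²), about 293 events, which is more than all 280 participants. At 70% events, HR 1.40 has 71.2% power with N = 320 and 76.1% with N = 360, so no sample size in the table reaches 80% for it.

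**The case against.** Four objections deserve an answer.

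*The printed row does not strictly violate ordering.* Power should fall when both the sample and the hazard ratio fall, and it does, from 84% and 83% to 82%. This stands: the side-by-side comparison raises suspicion, but showing that the drop is far too small needs a power model. The scaling check above needs only the usual dependence on events and log hazard ratio.

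*The authors' formula is unknown.* True, and the five agreeing rows match closely rather than exactly, all slightly below the printed values. A consistent offset of up to 1.2 points cannot explain a gap of about 17. For the same reason, nothing should be made of the 360 statement: HR 1.46 computes to 79.4% at 60% events and 85.2% at 70%, which agrees with the text's approximate wording within the precision of this check.

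*The hazard ratio may not be the misprinted entry.* The documents cannot show the cause; the error could be in the printed power. That does not save the prose. A binary covariate's standard deviation cannot exceed 0.5, and even 80% power at 1.40 needs about 278 events, so 1.40 is not detectable at that power with 280 participants and 60-70% events.

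*The row is immaterial.* SAP 5.5.1 says: "There are no hypotheses being evaluated in this observational study with solely descriptive primary objectives, thus no formal statistical testing will be conducted". Protocol 13.2 also disclaims formal sample size and power calculations, and 280 is below the target. This limits the severity but leaves the stated figure wrong.

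**Conclusion.** The concern holds, as a minor error. One of six rows in Table 1 is wrong in both documents: its power is about 65% (64.4-66.3% allowing for rounding), not 82%, and the text repeats the error as the lower end of its range. This rests on the standard Cox formula at two-sided 5%, supported by the five rows it reproduces and by scaling from the neighbouring rows.

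The mislabelled column is a likely inference, not a proven fact. It rests on the implausible size of the values in days, the statement in Protocol 2.3, and the agreement of five rows on that reading. The site-count conflict in the SAP is plain but separate: 5 × 60 = 300, not 360.

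**What to change.** In SAP 3.2.4 and Protocol 13.2.3:

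1. Re-run and correct the row for 280 participants and 70% events. With its other inputs unchanged, HR 1.50 has 81% power and HR 1.51 has 82%.
2. Change the range in the text for 280 participants to about 1.50-1.75.
3. Confirm that the last column, and the matching sentence, mean the standard deviation of the binary covariate named in Protocol 2.3, and relabel both. If confirmed, state that the 1.75 end assumes a 20:80 split and the other rows 50:50. For comparison, 280 participants with 60% events and SD 0.5 could detect exp(2.802 / (0.5 × √168)) = 1.54 at 80% power.
4. State the formula used for the table.

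As a separate edit, reconcile the SAP's five sites (1.2, 3.2.2) with its approximately six sites (3.2.3) and its total of about 360 (1.6, 3.2.1).

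The cost is one row, two sentences, one column label and a line naming the formula in each document, plus the site-count edit. No enrolment or analysis changes. The stated detectable hazard ratio for 280 participants at 70% events becomes less favourable, about 1.50 instead of 1.40.

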### 3.3 Software

All analyses will be performed utilizing SAS® version 9.3 or higher. All statistical tests will be conducted at the 5% Type I error rate (two-sided). When multiple tests are conducted, the chance of finding a significant difference in one of the tests, when in fact no difference exists, is greater than the stated Type I error rate. The investigators are aware of the multiple testing issues and will interpret results with caution and use confidence intervals where possible.

### 3.4 Analysis Populations

As this is an observational study, all available data will be analyzed.

### 3.5 Distributional Assumption Tests

Empirical distributions of all variables will be visually inspected to detect outliers. The underlying proposed statistical methods for each analysis will be examined, primarily through inspection of graphical displays, standardized residuals, or influence diagnostics. Where appropriate, transformations will be utilized or analyses will be performed utilizing a more appropriate distribution.

#### **4.0 ANALYSES OF DEMOGRAPHIC AND BASELINE DATA**

Baseline demographic variables (gender, age, race, ethnicity, educational level, employment status, and marital status) will be summarized for participants enrolled in the ancillary study. Descriptive summaries of the distribution of continuous baseline variables will be presented with percentiles (median, 25th and 75th percentiles), and with mean and standard deviation. Categorical variables will be summarized in terms of frequencies and percentages.

## **5.0 STATISTICAL ANALYSES**

The primary objective of this study is to estimate opioid use rates, via various measures of use (Section 2), overall and separately for the sub-groups defined. Secondary exploratory analyses will involve modeling of opioid use as a function of certain independent predictors. For the primary objective all continuous variables (e.g., percent use days in the first week) will be summarized using the following descriptive statistics: *n* (non-missing sample size), mean, standard deviation, median, maximum and minimum. The frequency and percentages (based on the group-specific sample size) of observed levels will be reported for all categorical measures.

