## **6.0 MISSING DATA**

The number of missing as well as the number of positive and negative UDSs will be tabulated separately when calculating the UDS outcome at baseline, and weeks 1, 4 and 8. Analyses of self-reported use time to event outcomes (e.g. time to first use) will impute intermittent missing days as use, but will not impute missing days due to drop-out or loss-to-follow-up. When tallying the days of opioid use, all missing self-reported days will be imputed as positive. The number of days imputed for each subject will also be summarized.

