**Table 7: Listing of Adverse Events by CTP**

CTP	Participant ID	AE Description	Onset Date	Severity of Overdose	Opioids Involved	Primary Cause of Death	Aware Date	Hospitalization

[figure not shown]
Table 8: Summary of Time to First Use by Type of Treatment Received Post-Discharge			
	Treatment Type Received Post-Discharge		
	Medication-assisted Treatment	No medication-assisted Treatment	Total
Number of Participants			
Any Opioid Use			
Yes			
No			
Time to First Use  (days)			
N			
Mean			
SD			
Median			
Min			
Max			

---

 Time to first use summary statistics are only summarized for subjects who reported any opioid use on TLFB.

**Figure 2:** Kaplan-Meier Plots of Time to First Use by Type of Treatment Received

*Example Kaplan-Meier figure provided below.*

The x-axis for the Time to First Use Kaplan-Meier Plots will be measured in days. Separate curves on the same plot will be defined as the types of treatment received. Censored observations will be represented using a + sign.

[figure not shown]
Table 9: Summary of Time to First Use by Length of Stay				
	Length of Stay			
	≤7 days	8-20 days	≥21 days	Total
Number of Participants				
Any Opioid Use				
Yes				
No				
Time to First Use  (days)				
N				
Mean				
SD				
Median				
Min				
Max				

---

 Time to first use summary statistics are only summarized for subjects who reported any opioid use on TLFB.

**Figure 3:** Kaplan-Meier Plots of Time to First Use by Length of Stay

*Example Kaplan-Meier figure provided below.*

The x-axis for the Time to First Use Kaplan-Meier Plots will be measured in days. Separate curves on the same plot will be defined as the length of stay categories. Censored observations will be represented using a + sign.

[figure not shown]
Table 10: Summary of Time to First Use by Baseline Opioid Use Severity			
	Baseline Opioid Use Severity		
	Low Severity	High Severity	Total
Number of Participants			
Any Opioid Use			
Yes			
No			
Time to First Use  (days)			
N			
Mean			
SD			
Median			
Min			
Max			

---

 Time to first use summary statistics are only summarized for subjects who reported any opioid use on TLFB.

**Figure 4:** Kaplan-Meier Plots of Time to First Use by Baseline Opioid Use Severity

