Any Regular Opioid Use			
Yes			
No			
Time to Regular Opioid Use  (days)			
N			
Mean			
SD			
Median			
Min			
Max			

---

 Time to regular opioid use summary statistics are only summarized for subjects who reported seven consecutive opioid use days on TLFB.

**Figure 7:** Kaplan-Meier Plots of Time to Regular Opioid Use by Baseline Opioid Use Severity

*Example Kaplan-Meier figure provided below.*

The x-axis for the Time to Regular Opioid Use Kaplan-Meier Plots will be measured in days. Separate curves on the same plot will be defined as the baseline opioid use severity. Censored observations will be represented using a + sign.

Table 14: Summary of UDS Results by Type of Treatment Received Post-Discharge			
	Treatment Type Received Post-Discharge		
	Medication-assisted Treatment	No Medication-assisted Treatment	Total
Number of Participants			
UDS Result (Baseline  )			
Negative			
Positive			
Missing			
UDS Result (Week 1)			
Negative			
Positive			
Missing			
UDS Result (Week 4)			
Negative			
Positive			
Missing			
UDS Result (Week 8)			
Negative			
Positive			
Missing			

---

 Day of Discharge into Community

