**Table 17: Summary of Days of Opioid Use by Type of Treatment Received Post-Discharge**

	Treatment Type Received Post-Discharge		
	Medication-assisted Treatment	No Medication-assisted Treatment	Total
Days of Opioid Use  up to Week 8			
N			
Mean			
SD			
Median			
Min			
Max			
Subjects Abstinent up to Week 8 N(%)			
Number of Imputed Days Per Subject (up to Week 8)			
N			
Mean			
SD			
Median			
Min			
Max			

---

 All missing self-reported use is imputed as positive.

Table 18: Summary of Days of Opioid Use by Length of Stay				
	Length of Stay			
	≤7 days	8-20 days	≥21 days	Total
Number of Participants				
Days of Opioid Use  up to Week 1				
N				
Mean				
SD				
Median				
Min				
Max				
Subjects Abstinent up to Week 1 N(%)				
Number of Imputed Days Per Subject (up to Week 1)				
N				
Mean				
SD				
Median				
Min				
Max				
Days of Opioid Use  up to Week 4				
N				
Mean				
SD				
Median				
Min				
Max				
Subjects Abstinent up to Week 4 N(%)				
Number of Imputed Days Per Subject (up to Week 4)				
N				
Mean				
SD				
Median				
Min				
Max				

 All missing self-reported use is imputed as positive.

 All missing self-reported use is imputed as positive.

Table 18: Summary of Days of Opioid Use by Length of Stay				
	Length of Stay			
	≤7 days	8-20 days	≥21 days	Total
Days of Opioid Use  up to Week 8				
N				
Mean				
SD				
Median				
Min				
Max				
Subjects Abstinent up to Week 8 N(%)				
Number of Imputed Days Per Subject (up to Week 8)				
N				
Mean				
SD				
Median				
Min				
Max				

---

 All missing self-reported use is imputed as positive.

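### SAP Tables 8-13 count participants lost before Week 8 without the event as non-events, so the tabulated Yes percentage for any use and any regular use is a lower bound, and no Week 8 Kaplan-Meier rate is tabulated beside it

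*SAP*

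**What the plan says.** SAP section 5.0 sets the percentage base for categorical rows: "The frequency and percentages (based on the group-specific sample size) of observed levels will be reported for all categorical measures". For continuous variables the same paragraph reports a non-missing sample size, so the two bases differ.

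Tables 8-10 give the number of participants and then the row "Any Opioid Use", with levels Yes and No. Tables 11-13 do the same for "Any Regular Opioid Use". Neither row has a missing, unknown or censored level.

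SAP section 3.4 excludes nobody: "As this is an observational study, all available data will be analyzed".

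SAP section 6.0 has two rules for missing self-report:
- For time-to-event outcomes, intermittent missing days are imputed as use, "but will not impute missing days due to drop-out or loss-to-follow-up".
- For day counts, "When tallying the days of opioid use, all missing self-reported days will be imputed as positive". The footnotes to Tables 17-19 repeat this: "All missing self-reported use is imputed as positive".

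Tables 17-19 also carry the row "Subjects Abstinent up to Week 8 N" (with a percentage). It has no footnote of its own.

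Figures 2-7 are Kaplan-Meier plots with censoring marks, and SAP section 5.5 plans Cox models. The time summaries in Tables 8-13 are confined by footnote to participants with reported use. No table shell holds a Kaplan-Meier estimate at Week 8.

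**The concern.** The primary objective is to estimate rates of opioid use after discharge. For first use and regular use, the only rate in the table shells is the crude Yes percentage. A participant lost at Week 1 with no use reported has an unknown 8-week status, but lowers that percentage just as an observed abstainer would.

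This has two consequences. First, the tabulated rate falls short of the 8-week rate by the share of participants who are lost and have the event later. Second, when loss differs between subgroups, part of any contrast in Tables 8-13 may reflect retention. This could matter for the treatment comparison: SAP section 2.3 assigns medication-assisted treatment from the Week 1, 4 and 8 visits, so someone with no post-discharge visit has no route into that group.

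For any use there is also a question of consistency. If the day-count rule governs the abstinence rows of Tables 17-19, the same lost participant is not abstinent there. The No percentage in Tables 8-10 and the abstinent percentage in Tables 17-19 would then disagree, with nothing in the report to reconcile them.

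**Working it through.** The plan states no figure on this point, so there is none to reproduce. The documents also give no expected loss rate and no rate of use among those lost; both are assumptions below.

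**Definitions.** Let *a* be the share whose TLFB ends before Week 8, *u* the share of those followed to Week 8 who have the event, and *r* the share of those lost who had the event before their last TLFB. For any use:
- Yes in Tables 8-10 = (1 − a)u + a·r
- Not Yes = 1 − Yes
- Abstinent to Week 8 in Tables 17-19, if all missing days count as use = (1 − a)(1 − u)
- Gap between the last two = a(1 − r), which does not depend on *u*

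If a share *v* of those lost (v ≥ r) would have the event by Week 8, the true rate is (1 − a)u + a·v, and Yes understates it by a(v − r). The gap a(1 − r) is therefore the largest possible understatement, not the bias itself.

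**Illustration 1.** u = 0.70, the upper end of the 60-70% in SAP section 3.2.4, applied here to those followed to Week 8.

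| Loss a | r | Yes | Not Yes | Abstinent (Tables 17-19) | Gap |
|---|---|---|---|---|---|
| 10% | 30% | 66% | 34% | 27% | 7 |
| 30% | 30% | 58% | 42% | 21% | 21 |
| 40% | 30% | 54% | 46% | 18% | 28 |
| 10% | 70% | 70% | 30% | 27% | 3 |
| 30% | 70% | 70% | 30% | 21% | 9 |
| 40% | 70% | 70% | 30% | 18% | 12 |

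Example (30% loss, r = 30%): Yes = 0.70 × 0.70 + 0.30 × 0.30 = 0.58; abstinent = 0.70 × 0.30 = 0.21; gap = 0.30 × 0.70 = 0.21.

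**Illustration 2.** N = 360, true 8-week use 65%, exponential time to first use, and loss independent of use, with the last TLFB day split equally between Days 0, 7 and 28. The share still without use at those days is 1, 0.35^(7/56) = 0.877 and 0.35^(28/56) = 0.592, mean 0.823, so r is about 18%.

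| Loss | Yes in Table 8 | Use implied by Table 17 | Lost without reported use |
|---|---|---|---|
| 10% | 60.3% | 68.5% | 8.2% (about 30 people) |
| 20% | 55.5% | 72.0% | 16.5% (about 59) |
| 30% | 50.8% | 75.5% | 24.7% (about 89) |
| 40% | 46.1% | 79.0% | 32.9% (about 118) |

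Here the true rate is known to be 65%, so Yes is low by 4.7 to 18.9 points. Varying true use over 60-70% puts the gap between the two table sets at about 8 to 34 points.

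**Subgroups.** Two groups with the same true use of 65% but losses of 10% and 30% would show 60.3% against 50.8% Yes in Table 8, and 68.5% against 75.5% use in Table 17. Neither difference is real, and they point in opposite directions.

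**The case against.** The strongest reply is that the plan already handles censoring. Tables 8-13 are each paired with a Kaplan-Meier plot, and modelling is by Cox regression. This stands: the fault lies in the crude rows, not in every time-to-event result. It does not remove the fault, because no 8-week estimate from those curves reaches a table.

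Several stronger readings are tempting but unsupported:
- *The SAP puts lost participants under No.* No text says so, and section 5.0 speaks of observed levels. But if they were printed in neither row, the Yes percentage would not change, since the base is still the whole group.
- *Tables 11-13 also conflict with Tables 17-19.* They do not. Tables 17-19 have no regular-use row, and being neither abstinent nor a regular user is a coherent status.
- *A missing urine screen in Tables 14-16 is a third contradictory status.* It is a different measure, and Protocol section 10.10 allows telephone assessment, which can give self-report without urine.
- *The two imputation rules are a hidden inconsistency.* Section 6.0 declares both, and Tables 17-19 report imputed days. What is unstated is how lost participants are classed in Tables 8-13, and whether the day-count rule governs the abstinence rows.
- *More loss always lowers Yes.* The slope of Yes on loss is r − u. It is zero when r = u and reversed when r > u.

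Also, each later TLFB covers every day since the previous one, so a missed interim visit can be recovered. Only terminal loss matters.

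**Conclusion.** The point holds in this form. As written, the Yes percentage in Tables 8-13 is a lower bound, under the section 6.0 event rule, for the 8-week rate of first use and of regular use. It understates that rate whenever some of those lost without the event have it later, and it can distort subgroup contrasts when loss differs. The irreconcilable figures apply only to any use (Tables 8-10 against Tables 17-19), and only if the day-count rule governs the abstinence rows, as section 6.0 implies but does not state.

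The size cannot be fixed from the documents. The gap is (share lost) × (share of the lost without a reported event): 3-12 points when 70% of those lost had reported use first, and 7-28 points when 30% had, over an assumed 10-40% loss. It deserves correction because it bears on the primary-objective rate and the curves needed for the repair are already planned.

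**What to change.** In Tables 8-13 replace Yes/No with three levels:
- Event, under the section 6.0 time-to-event rule, including imputed intermittent days
- No event, followed to Week 8
- No event, censored before Week 8

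The event is first use in Tables 8-10 and seven consecutive use days in Tables 11-13, so a participant with some use but no seven-day run before loss falls in the third level of Tables 11-13.

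Report the Week 8 Kaplan-Meier cumulative rate with a 95% confidence interval, overall and by subgroup, as the estimated rate. State that it assumes loss independent of use. Beside it, label the crude Yes percentage as a lower bound and Yes plus censored as an upper bound. Dropping the censored from the denominator is no cure: in Illustration 2 at 20% loss it gives 55.5/(55.5 + 28.0) = 66.5% against a true 65%.

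In Tables 17-19 keep the SAP's declared day-count rule, state that it also governs the abstinence rows, and show how many participants are non-abstinent only because of imputed days.

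The cost is table-shell wording and minor programming, with no new data. The downside is a few more rows and a range beside the single figure.
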